4.7.1.3. Events Causing Death

The observation periods for patient deaths are per the observation periods defined above.

- Death on-treatment: deaths occurring during the TEAE period,
- Death post-treatment: deaths occurring during the post-treatment period.

4.7.2. Clinical Laboratory Safety Variables

Clinical laboratory tests will consist of blood analyses (including hematology and clinical chemistry) and urinalysis. Clinical laboratory values will be converted and analyzed in international units, including associated normal ranges provided by the central laboratory. International units will be used in all listings and tables. Clinical laboratory values in conventional (US) units will also be available in the database, with associated normal ranges (analyses can be provided upon request). Both actual test values and “change from baseline” values (defined as the post-baseline value minus the baseline value) will be used in the result summaries. Potentially clinically significant abnormalities (PCSA) ranges will be applied to the laboratory test values as applicable (see Appendix 10.3 for PCSA definitions).

Unless otherwise specified below, blood samples for clinical laboratories will be collected at the protocol scheduled visits, and visits will be assigned to the Analysis Windows (See Appendix 10.2). The laboratory parameters (excluding those considered as efficacy parameters) will be classified as follows:

- Hematology:
 - Red blood cells and platelets: hemoglobin, hematocrit, erythrocytes count, platelets count, reticulocyte count, ery. mean corpuscular Hemoglobin (MCH), ery. mean corpuscular HGB concentration (MCHC), ery. mean corpuscular volume (MCV)
 - White blood cells: white blood cell count, neutrophils, lymphocytes, monocytes, basophils, eosinophils
- Clinical chemistry:
 - Metabolism: glucose, total protein, albumin, creatine phosphokinase

- Electrolytes: sodium, potassium, chloride, calcium, phosphorus, bicarbonate
- Renal function: creatinine, creatinine clearance, blood urea nitrogen (BUN), uric acid
- Liver function: alanine Aminotransferase (ALT), aspartate aminotransferases (AST), alkaline phosphatase (ALP), GGT, bilirubin, LDH
- Hepatitis screen: anti-hepatitis-C antibody and hepatitis B surface antigen collected at week -3 and week 96.

4.7.3. Vital Sign Variables

Vital signs parameters will include height (cm), weight (kg), heart rate (bpm), systolic and diastolic blood pressure (mmHg) after resting at least five minutes. Both actual test values and “change from baseline” values (defined as the post-baseline value minus the baseline value) will be provided for protocol specified visits and visits will be assigned to the Analysis Windows (See Appendix 10.2). Potentially clinically significant Abnormalities (PCSA) ranges will be applied to the vital sign parameter values as applicable (see Appendix 10.3 for PCSA definitions).

4.8. Other Variables

Other assessment endpoints are listed and defined below. Protocol schedule visits will be assigned to the Analysis Windows (See Appendix 10.2).

- The percent change in hs-CRP from baseline to protocol specified visits. Hs-CRP values greater or equal to 10 mg/L will be excluded from analyses in a second approach, since these are suggestive of concurrent infection(1). PCSA (potentially clinically significant abnormalities) criteria for hs-CRP are listed in Appendix 10.3.
- The absolute change in HbA1c (%) from baseline to protocol specified visits. PCSA criteria for HbA1c are listed in Appendix 10.3.
- The proportion of patients with two consecutive results, separated by at least 21 days, of calculated LDL-C <25 mg/dL (<0.65 mmol/L) (and again for calculated LDL-C <15 mg/dL [< 0.39 mmol/L]) during the treatment period.
- The proportion of patients with at least one result of calculated LDL-C <25 mg/dL (<0.65 mmol/L) (and again for calculated LDL-C <15 mg/dL [< 0.39 mmol/L]) during the treatment period.
- For the patients with two consecutive results as described above, the time to the first calculated LDL-C <25 mg/dL (<0.65 mmol/L) (and again for calculated LDL-C <15 mg/dL [< 0.39 mmol/L]) during the treatment period.

- Gonadal hormone levels (for female patients - estradiol, follicle-stimulating hormone (FSH) and luteinizing hormone (LH); for male patients - testosterone, FSH and LH)

4.9. Anti-Drug Antibody Variables

Anti-drug (Praluent) antibody (ADA) are assessed at baseline (before the first study treatment injection), at weeks 48 and 96. ADA measurements will be assigned to the analysis windows as defined in Appendix 10.2. As appropriate, patient frequencies and percentages will be depicted, and the percentages will be calculated based on the ADA population.

The following variables will be described:

- ADA response (Positive or Negative). For ADA positive:
 - Titer levels
 - Neutralizing status (Positive or Negative)
- Pre-existing positive ADA defined as patients with positive ADA response at baseline with less than 4-fold increase in titer in the post-baseline period
- Treatment-emergent positive ADA response defined as 1) Patients with no ADA positive response at baseline but with any positive response in the post-baseline period or 2) Patients with a positive ADA response at baseline and at least a 4-fold increase in titer in the post-baseline period. For treatment-emergent positive ADA, the following categories for ADA duration will be applied:
 - A persistent positive response is a treatment-emergent ADA positive response detected in at least 2 consecutive post-baseline samples separated by at least a 12-week period
 - An indeterminate duration positive response is defined as ADA present only at the last sampling time point
 - A transient positive response is defined as any treatment-emergent positive ADA response that is neither considered persistent nor indeterminate

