7.3. Handling of Study Drug Discontinuation and Patient Withdrawal from the Study

7.3.1. Study Drug Discontinuation

Study drug should be continued whenever possible. In the event study drug dosing is stopped, it should be determined if the stop can be made temporarily. Permanent discontinuation should be a last resort. In any case, the patient should remain in the study as long as possible.

Patients who prematurely discontinue study drug should remain in the study and undergo all study visits and procedures, with the exception of dosing with study drug. At the time of study drug discontinuation, the patient should have, as soon as possible, an unscheduled visit with the assessments that are normally done at the end of study (EOS) visit (this should take place within 5 days of discontinuation of study drug, if possible), and then resume the original study schedule until end of study.

Assessment of patients who do not consent to remain in the study after discontinuation of study drug should be managed according to Section [7.4.1](#).

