5.9. Analysis of Anti-Drug Antibody Variables

The summary of ADA variables will be presented by treatment groups (Praluent, placebo) on the ADA population. No formal inferential testing will be performed. Summaries will be descriptive in nature.

ADA variables will be summarized, taking into account all samples regardless of timing in relation to injections. ADA results will be summarized as follows:

- ADA results (negative or positive) by time point
- Neutralizing status (negative or positive) by time point for positive ADA

- ADA titers using descriptive statistics (median, minimum and maximum) for positive ADA by time point
- Number (%) of patients with pre-existing ADA and number (%) of patients with treatment-emergent ADA positive response
- Number (%) of patients with persistent/indeterminate/transient treatment-emergent ADA positive response
- Time to onset of treatment-emergent ADA positive response using descriptive statistics.
- Number (%) of patients with at least 1 neutralizing ADA.

Correlations between ADA parameters (e.g., titers, treatment-emergent ADA positive status, neutralizing status) and safety and/or efficacy endpoints will also be explored (e.g., scatter plot).

[REDACTED] [REDACTED]
[REDACTED].

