6.6. Unscheduled Assessments

For efficacy, safety laboratory data, vital signs, physical examinations, and ADA, unscheduled visit measurements may be used to provide a measurement for a time point, a baseline, a last or a worst value, if appropriate according to their definitions. The measurements may also be used to determine abnormal values and PCSA.

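### Read literally, SAP 4.9's leftover definition of transient ADA can take in a few patients who are still antibody-positive at their last sample

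*SAP*

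**What the plan says.** SAP 4.9 says that ADA samples "are assessed at baseline (before the first study treatment injection), at weeks 48 and 96". A response is treatment-emergent in either of two ways: the patient is negative at baseline and positive at any later sample, or belongs to the group described as "Patients with a positive ADA response at baseline and at least a 4-fold increase in titer in the post-baseline period".

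Three duration categories follow:

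- Persistent is a treatment-emergent response "detected in at least 2 consecutive post-baseline samples separated by at least a 12-week period".
- For indeterminate: "An indeterminate duration positive response is defined as ADA present only at the last sampling time point".
- For transient: "A transient positive response is defined as any treatment-emergent positive ADA response that is neither considered persistent nor indeterminate".

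Off-schedule ADA samples can arise. Protocol 7.3.1 asks that patients who stop study drug have "an unscheduled visit with the assessments that are normally done at the end of study (EOS) visit", and then return to the schedule. Protocol Table 1 lists an ADA sample at that end-of-study visit. SAP 6.6 lets such results count: "For efficacy, safety laboratory data, vital signs, physical examinations, and ADA, unscheduled visit measurements may be used to provide a measurement for a time point".

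The SAP points two ways on how they count. Section 5.9 says: "ADA variables will be summarized, taking into account all samples regardless of timing in relation to injections". Section 4.9, however, assigns ADA measurements to the analysis windows of Appendix 10.2, and section 6.5 keeps one value per window, the one nearest the target day.

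SAP 5.9 reports the number and percentage in each duration category. It also reports ADA status, neutralizing status and titers by time point. All of this is descriptive.

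**The concern.** The word transient tells a reader that the response went away. The rule never checks that. It tests for persistence, then for one narrow form of unknown duration, and gives everyone else the label that implies resolution. A patient can therefore be positive at the last sample, fail both tests on a technicality, and be counted as transient when the data show only that the duration is unknown.

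What is at stake is the split between transient and indeterminate in one descriptive safety table. The patients concerned are mainly those with boosted pre-existing antibodies and those with a discontinuation sample.

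**Working it through.** The plan gives no figure to reproduce here, so the check applies the three definitions to every possible sequence of results.

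**Inputs.** Scheduled post-baseline samples fall on day 337 (week 48) and day 673 (week 96), per Protocol Table 1. The gap is 673 − 337 = 336 days, or 48 weeks. The persistence threshold is 12 × 7 = 84 days. The windows in SAP Table 2 are days 85–252 (week 24), 253–420 (week 48), 421–588 (week 72) and 589–756 (week 96). A run of consecutive positives spanning at least 84 days is taken as persistent.

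**Step 1. Baseline-negative, scheduled samples only.** The last sampling time point is read as the patient's own last sample.

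| Week 48 | Week 96 | Category |
|---|---|---|
| + | + | persistent |
| − | + | indeterminate |
| missing | + | indeterminate |
| + | missing | indeterminate |
| + | − | transient |

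No patient who is positive at the last sample is called transient. The fourth row depends on the per-patient reading, which the SAP does not state. If the phrase means week 96, that patient falls to transient.

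**Step 2. Baseline-negative, one unscheduled sample U added.** Scheduled samples are held on their target days. The sequences that are positive at the last sample yet transient are:

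| Sequence | Days of U, all samples counted | Days of U, one value per window |
|---|---|---|
| week 48 +, U +, end | 338–420 | none |
| U +, week 48 +, end | 254–336 | none |
| U +, week 96 + (week 48 missing or −) | 590–672 | none |
| U +, week 48 −, week 96 + | 2–336 | 85–252 |
| week 48 +, U −, week 96 + | 338–672 | 421–588 |

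For example, take a patient positive at week 48 who stops drug at week 54, is positive at the discontinuation visit and then leaves. Week 54 is day 54 × 7 + 1 = 379, and 379 − 337 = 42 days, which is less than 84, so the response is not persistent. It was present at two samples, so it is not indeterminate. With all samples counted, it is transient. With one value per window, day 379 lies in the week 48 window, the day 337 value is kept, and the patient is indeterminate.

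The first three rows, the close pairs, vanish under windowing. The last two, positive-negative-positive, do not.

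**Step 3. Baseline-positive with a 4-fold rise.** Suppose week 48 is boosted and there is no later sample. One post-baseline sample cannot be persistent. Because ADA was also present at baseline, it was not literally present only at the last time point. The remainder is transient. The same holds for baseline positive, week 48 negative, week 96 positive and boosted. Neither case needs an unscheduled sample, and windowing does not alter either.

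**Step 4. Redefinition.** Call a non-persistent response indeterminate if it is still present at the last sample, and transient otherwise. Every baseline-negative sequence in Step 2 that was transient becomes indeterminate under both counting rules. No category in Step 1 changes.

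**The case against.** The strongest objection is the window rule. SAP 4.9 itself assigns ADA to windows, and 6.5 names ADA and says that the windows apply to all analyses. The phrase in 5.9 about all samples concerns timing relative to injections and can be read as leaving windowing in place. On that reading the close-pair route disappears when scheduled visits are on target. This stands as far as it goes. But the persistent rule is written in samples, 5.9 says all samples, and the SAP does not say which governs. Positive-negative-positive sequences survive either way, although the intervening negative gives the transient label some basis there.

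Second, the categories are introduced for treatment-emergent ADA. The indeterminate rule can therefore be read as treatment-emergent ADA seen only at the last time point, which would admit a boost first seen there. That is a sensible reading, so it would be wrong to infer that boosted patients can never be indeterminate. It is not what the sentence literally says, and a programmer could code it either way.

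Third, a reader might infer that every error is in the reassuring direction. The documents do not support that. If any positive sample counts towards persistence, a patient who is positive at baseline, positive but below a 4-fold rise at week 48, and boosted at week 96 would be persistent.

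Fourth, a remainder class is not an error in itself: it makes the categories exhaustive. Other outputs also limit the harm. Status and titers are reported by time point, and the ADA endpoint in Protocol 6.2.4 (status and titers at end of study) is untouched. That is right, though patients who leave before week 96 are absent from the week 96 row.

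**Conclusion.** The point holds as a minor defect of definition. The literal rule can attach a label implying resolution to a patient whose last sample is positive. This happens by the baseline-positive route, by the close-pair route if all samples count, and by positive-negative-positive sequences that include an unscheduled sample. Baseline-negative patients with scheduled samples only are classified correctly, provided that the last sampling time point means the patient's own.

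A reader might infer that the plan understates lasting immunogenicity. The documents do not support that. Correcting the rule moves patients from transient to indeterminate only; the persistent count and the treatment-emergent incidence stay the same.

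Nor can a percentage be attached. The documents give no ADA incidence, baseline positivity or boosting rate, and Protocol 7.3.1 asks patients who stop drug to stay on schedule, so a week 96 sample is intended. The number affected should be small, but it cannot be computed.

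**What to change.** In SAP 4.9, before database lock:

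- Define indeterminate as a treatment-emergent response (for baseline-positive patients, at least a 4-fold titer rise) that is still present at the patient's last evaluable sample and does not meet the persistent rule.
- Define transient as a treatment-emergent response that is no longer present at the patient's last evaluable sample and does not meet the persistent rule.
- State whether duration is classified on all samples or on one value per analysis window, and align 4.9, 5.9 and 6.5.

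The cost is two redefined sentences and one clarification. The transient count becomes slightly smaller and the indeterminate count slightly larger. No extra sampling is needed.

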5. STATISTICAL METHODS

5.1. Demographics and Baseline Characteristics

Demographic and baseline characteristics will be summarized descriptively by treatment group and overall for the safety population. Parameters described in Section 4.1 will be summarized for the safety population, the primary safety population in the case of a 10% difference (in any treatment group) from the number of safety population, and again for the ITT population in the case of a 10% difference (in any treatment group) from the number of safety population.

Continuous data will be summarized using the number of patients with data, mean, SD, median, minimum and maximum for each treatment group. First quartile (Q1) and third quartile (Q3) will be also provided for baseline lipid parameters, HbA1c and hs-CRP. Categorical and ordinal data will be summarized using the number and percentage of patients in each treatment group.

Treatment group comparisons for demographic characteristics and disease characteristics will be provided for descriptive purposes (i.e., confirmation of the randomization process to equally distribute relevant patient background profiles among the two treatment groups) using the Chi-square test for categorical data and the asymptotic one-way ANOVA test for Wilcoxon scores (Kruskal-Wallis test) for continuous data. As applicable, other safety baseline data is presented collectively in the descriptive statistics summary tables containing respective post-baseline data.

5.2. Medical History and Disease Characteristics

Medical history and disease characteristics will be descriptively summarized by treatment group and overall for the study in safety population.

All reported patient's medical history and surgical history will be presented by primary SOC and HLT. The tables will be sorted by SOC internationally agreed order and decreasing patient frequency of HLT based on the overall incidence in the study. In addition, all medical history of specific interest, as described in Section 4.2, will be summarized by patient incidence and percentage.

For the patients with primary CVD prevention status (see definition in Section 4.2), the number (and percentage) of patients with the following comorbidities/risk factors will be tabulated:

- Diabetes mellitus with target organ damage (renal damage (microalbuminuria, or macroalbuminuria, moderate CKD) and/or retinopathy (pre-proliferative or proliferative diabetic retinopathy and/or laser treatment for diabetic retinopathy)),
- Diabetes mellitus with 2 or more risk factors (see Section 4.2),

- Family History of premature CHD
- Hypertension,
- Moderate CKD
- Current smoker
- At least 2 of the above comorbidities/risk factors

In addition, smoking status will be summarized in patients with primary CVD prevention status.

For the patients with a secondary prevention status, the CVD history will be described using the number (%) of patients with:

- History of CHD (see Section 4.2)
- History of ischemic stroke
- History of PAD with severity criteria
 - Intermittent claudication and ankle brachial index ≤ 0.90
 - Peripheral revascularization procedure (angioplasty, stenting) for PAD
 - Thrombolysis for PAD
 - Peripheral revascularization surgery (arterial bypass) for PAD
 - Critical limb ischemia

Additionally:

- The number (%) of patients with a secondary prevention status with 1 or more associated comorbidity among hypertension, diabetes mellitus, and/or moderate CKD will be summarized.
- The number (%) of patients with history of CHD and 1 or more associated comorbidity among hypertension, diabetes mellitus, moderate CKD and/or other CVD (ischemic stroke, PAD) will be summarized.

For patient disease characteristics, as described in Section 4.2, continuous data will be summarized using the number of patients with data, mean, SD, median, minimum and maximum for the study and for each of the strata. Categorical and ordinal data will be summarized using the number and percentage of patients in the study and for each stratum.

5.3. Prior and Concomitant Medications

All prior medications, dictionary coded by WHO-DD, will be descriptively summarized by treatment group and overall for the study, for patients in the safety population. Summaries will present patient counts (and percentages) for all prior medications, by decreasing frequency of the overall incidence of ATC followed by therapeutic class. In case of equal frequency across anatomic or therapeutic categories, alphabetical order will be used. Patients will be counted once in each ATC category (anatomic or therapeutic) linked to the medication, but may be counted several times for the same medication.

All concomitant medications during the treatment period, dictionary coded by WHO-DD, will be descriptively summarized by treatment group, for patients in the safety population. Summaries will present patient counts (and percentages) for the concomitant medication groups described in Section 4.3 for all concomitant medications (including statin, non-statin LMT, CV), by decreasing frequency of the Praluent group incidence of ATC followed by therapeutic class. In case of equal frequency across anatomic or therapeutic categories, alphabetical order will be used. Patients will be counted once in each ATC category (anatomic or therapeutic) linked to the medication, hence may be counted several times for the same medication. Additionally, concomitant medications pre-specified as statin, non-statin LMT, and CV will be summarized by patient counts (and percentages) by therapeutic class or e-CRF pre-specified categories as appropriate and standardized medication name.

Post-treatment medications will be summarized as described above for all medications.

LMT (statins and other LMTs) use after randomization will be summarized over time graphically by treatment group and LMTs intensity at randomization using the following categories:

- atorvastatin 40 to 80 mg daily or rosuvastatin 20 to 40 mg daily or;
- atorvastatin below 40 mg daily or rosuvastatin below 20 mg daily or simvastatin at any daily dose, or other statins,
- LMT other than statin only,
- no LMT.

The LMTs intensity at randomization is defined as:

- patients treated at randomization with atorvastatin 40 to 80 mg daily or rosuvastatin 20 to 40 mg daily (high intensity statin),
- patients treated at randomization with atorvastatin below 40 mg daily or rosuvastatin below 20 mg daily or simvastatin at any daily dose (low intensity statin), or other statins,

- non-statin LMT only,
- no LMT.

